Project proposal for the PhD project:

Psychiatric comorbidity in Back Pain Disorders
– Risk, treatment and pharmaco-epidemiological analysis

Applicant

[name], MscPH

Medical Research Department, Spine Centre of Southern Denmark

Last update: 29 of January 2019

Introduction

Chronic pain is a common health problem negatively affecting sleep, work ability and socialization¹⁻⁴. Chronic pain also increases morbidity, mortality and health care costs and has a direct and severe impact on the quality of life^{3 5-8}. The prevalence of chronic pain is up to 46,5% in the general population⁵. Musculoskeletal back and neck pain are one of the most common pain conditions^{2 9} with a lifetime prevalence of low back pain in the range of 51%-84%⁶. Variation in prevalence estimates can be explained by a difference in the definition of pain, research methodologies and differences in study samples¹⁰.

Several different diagnostic classifications systems for back pain disorders (BPD) exist, but most frequently these are divided into specific and non-specific BPD¹¹. This study chooses to establish two subgroups for specific BPD based on the presumed cause of illness and available treatment options and one group for unspecified BPD (UBD). The specific subgroups consists of inflammatory back diseases (IBD) and degenerative back diseases (DBD)¹².

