Psychiatric comorbidity will be defined as the presence of any of the following diagnosis, according to ICD-10 classification³⁰, obtained from the National Patient Registry – Psychiatry (NPD-Psych), covering all inpatient and outpatient psychiatric services in Denmark in the time period 1th January 2007 to 31th December 2017: Organic, including symptomatic, mental disorders (F00-DF09), Mental and behavioral disorders due to psychoactive substance use (F10-F19), Schizophrenia, schizotypal and delusional disorders (F20-F29), Mood [affective] disorders (F30-F39), Neurotic, stress-related and somatoform disorders (F40-F48), Behavioral syndromes associated with physiological disturbances and physical factors (F50-F59), Disorders of adult personality and behavior (F60-F69), Mental retardation (F70-F79), Disorders of psychological development (F80-F89), Behavioral and emotional disorders with onset usually occurring in childhood and adolescence (F90-F98) and, Unspecified mental disorder (F99). To qualify as a psychiatric comorbidity to back pain disorder, we define that the psychiatric diagnosis must be given no earlier than three years prior to back pain disorder diagnosis and no later than three years after.

Study 1) Prevalence of psychiatric comorbidity in back pain disorders

Psychiatric comorbidity in Back Pain Disorders
Risk, treatment and pharmaco-epidemiological analysis

Aim: 1) To estimate prevalence of psychiatric comorbidity in patients with BPD compared to patients without BPD and 2) To estimate prevalence of psychiatric comorbidity in patients with unspecific back pain (UBP) compared to the background population and to patients with a specific back pain (SBP) in a Danish nationwide cohort from 2010-2014.

Hypothesis: 1) There is a higher risk of psychiatric comorbidity in BPD patients compared to the background population and 2) UBP patients have a higher risk of psychiatric comorbidity compared to patients with specific BPD.

Design: The study will be a nationwide register-based matched cohort study.

Procedure: Selected BPD patients with the following diagnosis will be identified via the DNPR: Spondylopathies DM45-49, Other dorsopathies DM 50-54 and Segmental and somatic dysfunction DM99. Each patient will be matched 1:5 on age and sex with patients without back disorders by random at Statistics Denmark³⁸. The selection of diagnosis is to be able to match the population with non-BPD patients in the Danish registries.

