Information on somatic comorbidity for calculation of Charlson Comorbidity index³⁹ (CCI) at time of BPD diagnosis, will be retrieved from the DNPR. Data on psychiatric comorbidity will be identified using NPD-Psych. Information on marital status, vital status, and immigration status will be retrieved from the Civil Registration System (CPR)³⁵. Patients that are not alive or have emigrated within three years after BPD diagnosis are considered lost to follow-up and excluded from the cohort. Descriptive data on the socioeconomic status, education level and equivalent available income will be retrieved from Statistics Denmark³⁸. All data comprising each variable will be retrieved from 1th of January 2007 to 31th of December 2017 (three years before and after study period).

Measures of outcome: Primary outcome is to estimate prevalence of psychiatric comorbidity in patients with BPD compared to the Danish background population. Secondary outcome is to estimate prevalence of psychiatric comorbidity stratified by type of BPD (SBP UBP) compared to the Danish background population. We will use a presence of psychiatric comorbidity as outcome.

Statistics: We will use Fisher's exact test and t-test to compare baseline characteristics with 95% confidence intervals (CI) and p-values. Crude risks of psychiatric comorbidity will be calculated and logistic regression model will be used, to investigate differences between the distribution of risk in BPD patients and the background population. A logistic regression model will also be used to investigate differences between the distribution of psychiatric comorbidity in the IBD, DBD and UBP group compared to the background population. The logistic regressions will be reported using 95% CI and adjusted for the following confounders: age, sex, equivalent available income, educational level, CCI, marital status.

Study 2) The effect of psychiatric comorbidity on type of treatment for BPD

Aim: 1) To investigate whether treatment of BPD in patients with psychiatric comorbidity differ from treatment of patients with BPD without psychiatric comorbidity; 2) To investigate whether treatment of BPD differs in the following subgroups: a) specific BPD and no psychiatric comorbidity; b) specific BPD with psychiatric comorbidity; c) unspecific BPD with no psychiatric comorbidity; d) unspecific BPD with psychiatric comorbidity. Investigation will be performed in a nationwide Danish cohort in 2010-2014.

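### Study 1's any-diagnosis outcome includes somatoform disorders, which may label the same complaint as unspecific back pain; a sensitivity analysis without them is needed to interpret hypothesis 2

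*Combined protocol and SAP*

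**What the plan says.** The outcome is defined under Setting and study population: "Psychiatric comorbidity will be defined as the presence of any of the following diagnosis". The list covers the whole F-chapter and includes "Neurotic, stress-related and somatoform disorders (F40-F48" with no subcode removed. On timing, "the psychiatric diagnosis must be given no earlier than three years prior to back pain disorder diagnosis and no later than three years after". The diagnoses come from the psychiatric part of the patient registry, described as "covering all inpatient and outpatient psychiatric services in Denmark".

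Study 1, Measures of outcome, reduces this to any versus none: "We will use a presence of psychiatric comorbidity as outcome". Its second hypothesis is that "UBP patients have a higher risk of psychiatric comorbidity compared to patients with specific BPD".

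On the grouping, the Introduction sets up "two subgroups for specific BPD based on the presumed cause of illness and available treatment options and one group for unspecified BPD (UBD"; Study 1 calls the last group UBP. The Procedure gives the entry codes as "Spondylopathies DM45-49, Other dorsopathies DM 50-54 and Segmental and somatic dysfunction DM99" but does not say which of them form the inflammatory (IBD), degenerative (DBD) and unspecific groups.

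The Study 1 Statistics paragraph compares IBD, DBD and UBP with the background population by logistic regression, adjusted for age, sex, income, education, Charlson index and marital status. No analysis separates somatoform diagnoses from the rest.

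**The concern.** Specific back pain is grouped by presumed cause, and UBP is the group without a specified one. A somatoform diagnosis means, as a category, physical symptoms that physical disease does not adequately explain. What sets UBP apart is therefore close to a condition for one of the outcome diagnoses. A patient whose pain is coded as unspecific in the somatic register and as somatoform in the psychiatric register counts as having a comorbidity, although both codes may describe one complaint. The window runs three years in both directions, so it does not matter which label came first.

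At stake is the reading of hypothesis 2. If such double labelling is commoner in UBP than in IBD or DBD, the result moves in the predicted direction. The single binary outcome cannot then tell two codes for one complaint from additional mental illness. None of the adjustment variables addresses this.

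**Working it through.** **What can be reproduced.** The documents give no sample size, prevalence, event count or effect size for Study 1. There is no planned figure to check, and what follows illustrates direction and range only.

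**Inputs, all assumed.**
- p0: prevalence of at least one non-somatoform F-diagnosis, set equal in UBP and specific back pain (true OR 1.00); 5%, 8% and 12% were tried.
- s_u and s_s: among patients with no other F-diagnosis, the share with a somatoform diagnosis, in UBP and specific back pain respectively.

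**Formulas.**
- Observed prevalence in UBP: a = p0 + (1 − p0) × s_u
- Observed prevalence in specific back pain: b = p0 + (1 − p0) × s_s
- OR = [a/(1 − a)] / [b/(1 − b)]

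**Worked example.** With p0 = 8%, s_u = 1%, s_s = 0.1%: a = 0.08 + 0.92 × 0.01 = 0.0892; b = 0.08 + 0.92 × 0.001 = 0.0809; OR = (0.0892/0.9108)/(0.0809/0.9191) = 1.11.

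| p0 | s_u | s_s | a | b | OR |
|---|---|---|---|---|---|
| 8% | 0.5% | 0.5% | 8.46% | 8.46% | 1.00 |
| 12% | 0.1% | 0.05% | 12.09% | 12.04% | 1.004 |
| 8% | 0.2% | 0.1% | 8.18% | 8.09% | 1.01 |
| 8% | 0.5% | 0.1% | 8.46% | 8.09% | 1.05 |
| 8% | 1% | 0.1% | 8.92% | 8.09% | 1.11 |
| 8% | 2% | 0.2% | 9.84% | 8.18% | 1.22 |
| 5% | 2% | 0.2% | 6.90% | 5.19% | 1.35 |

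Over all unequal shares tried, the OR ran from 1.004 to 1.35. With equal shares there is no artefact.

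**A second set of assumptions.** Take 8% with other diagnoses in both groups, and add somatoform-only patients as a percentage of all patients, 0.5% in specific back pain throughout:
- 1% in UBP: (0.09/0.91)/(0.085/0.915) = 1.06
- 2% in UBP: (0.10/0.90)/(0.085/0.915) = 1.20
- 3% in UBP: (0.11/0.89)/(0.085/0.915) = 1.33

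**Could such an artefact reach significance?** At two-sided 5% and p0 = 8%, 80% power needs 17,819 per group for the OR of 1.11 and 4,693 per group for the OR of 1.22. For the OR of 1.05, power is 56% at 50,000 per group. For the OR of 1.01 it is 11% even at 100,000 per group. The documents do not say how large the groups will be.

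**Does it matter that the models compare each group with the background population?** No. In crude terms, with common background odds c, the ratio of the two ORs is {[a/(1 − a)]/c} / {[b/(1 − b)]/c}. The c cancels and leaves the OR above, so the UBP OR rises relative to the IBD and DBD ORs by the same factor.

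**With somatoform diagnoses removed.** Both groups return to p0 and the OR to 1.00. This follows from setting p0 equal, so it confirms the mechanism but not its actual size.

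**The case against.** A reader might infer that hypothesis 2 is partly true by definition. The documents do not support that. A UBP code creates no outcome event: the outcome needs a separate diagnosis from psychiatric services, and the Introduction says the registry data pick up only severe psychiatric illness. Patients with IBD or DBD can receive a somatoform diagnosis too. Nor do the documents define UBP as unexplained pain, and they give no code list for it. Any bias depends on a higher somatoform-only share in UBP, which is an empirical matter on which the plan is silent.

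A reader might also infer that a nationwide cohort would make even a small artefact significant. At the low end of the range this fails, as the 11% power figure shows. The illustration also treats every excess somatoform diagnosis as a duplicate label and none as genuine comorbidity, so it gives an upper view for each set of shares.

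The inclusion is deliberate. The Introduction argues that every psychiatric diagnosis is relevant because it marks a vulnerable patient whose back pain may be harder to treat. For a descriptive prevalence this is a good reason, and it stands against replacing the outcome. Dropping genuine somatoform disorder altogether could bias hypothesis 2 the other way. The comparison by type of back pain is also a secondary outcome.

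What this does not answer is whether a UBP excess reflects additional mental illness or two codes for one complaint. The Introduction's mention of grouping by ICD-10 does not settle it either: the Study 1 outcome is any versus none, and the F40-F48 block would still mix somatoform with neurotic and stress-related disorders.

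**Conclusion.** The point holds as a possible overlap between the outcome and the definition of one subgroup. It is unaddressed in the plan, and where present it favours hypothesis 2. It affects the UBP versus specific comparison, and equally the UBP versus background OR when set beside the IBD and DBD ORs. Its size is unknown: about 1.00 to 1.35 on the OR scale under assumed inputs with no true difference. Two things carry the conclusion and are not stated in the documents: that a somatoform diagnosis can denote the same pain, which follows from the meaning of the category, and that somatoform-only diagnoses are commoner in UBP, which only the study's own data can show. This is not a flaw that invalidates Study 1, but without a check hypothesis 2 cannot be interpreted cleanly.

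**What to change.** Keep the all-F outcome as planned. Before analysis, add to the Study 1 Statistics paragraph:

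- A sensitivity analysis for the UBP versus specific comparison and for the IBD, DBD and UBP comparisons with the background population. It uses the same models and covariates, but a patient counts only if at least one F-diagnosis other than F45 (the ICD-10 somatoform category) is present. The paragraph names no direct UBP versus specific model, so that contrast should be written in as well.
- A separate line for F45 by back pain group, beside the all-F result.
- A statement that, if the UBP excess disappears without F45, it will not be interpreted as additional co-occurring mental illness.

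The cost is one recoded variable and one rerun, with no new data. The downside is small: the sensitivity analysis also drops genuine somatoform disorder unrelated to back pain, although the main result and the separate line still show it.

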When investigating psychiatric comorbidity in BPD patients, focusing on anxiety and depression, has been the norm. However, important information on the relationship between other types of mental illness and back pain disorders might be identified, if a dataset of sufficient size and quality, is used for analysis. A population-based set of registry data as the ones available in Denmark provides this. By grouping psychiatry comorbidity according to ICD-10, mental illnesses with common pathways are analyzed together. In the ICD-10 system psychiatric diagnosis are grouped according to symptomatology and common etiology³⁰. All psychiatric diagnoses are considered relevant in the chosen population, as any psychiatric disorders represents a vulnerable patient with possible complicating factors when treating back pain. The limitation of Danish registry-based data is, that it does not provide complete data from the primary care sector selecting only severe psychiatric diagnosis. In conclusion, back pain disorders and the association with psychiatric comorbidity has primarily been investigated using symptomatology, not ICD-10 diagnoses and with a focus on anxiety and depression. The studies are small, heterogeneous and of varying quality. The use of pharmacological treatment, including opioids, in back pain disorders complicated by psychiatric comorbidity is unknown.

Aim of the thesis

The aim of this PhD thesis is to use population-based registry data to:

1) to estimate the prevalence of psychiatric comorbidity in patients with back pain disorders (BPD) compared to patients with no back pain in the time period 2010-2014; 2) Investigate whether presence of psychiatric comorbidity affects utilization of pharmacological, surgical and other types of treatment for patients with BPD 3) Investigate whether presence of psychiatric comorbidity affects utilization and dosages of pharmacological treatment for patients with BPD.

Clinical contributions of this PhD

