Hypothesis: 1) Psychiatric comorbidity affects type of treatment in BPD patients and 2) psychiatric comorbidity affects type of treatment in subgroups of BPD.

Design and study population: The study will be a nationwide register-based cohort study. The study population consists of patients with BPD and in the sub-analysis the study population consists of patients with BPD and psychiatric comorbidity.

Procedure: BPD patients will be identified via the DNPR. Surgical treatment will be defined as the presence of any procedure code for back surgery retrieved from DNPR (NOMESCO: KNA-W)³⁴⁻⁴⁰. Pharmacological treatment of BPD will be defined as any treatment with the following drugs: NSAID (ATC: N01A*), acitomenophen (ATC: N02BE01), opioids (N02A*), antiepileptica (ATC: N03A) and tricyclic antidepressants (ATC: N06AA)¹³ identified using the Register of Medicinal Products Statistics⁷. Data on other types of treatment (defined as any treatment not surgical or pharmacological) such as physiotherapist, psychologist, chiropractor or occupational therapist (covered via tax-funded health insurance) will be obtained via The Danish National Health Insurance Service Register (SSR)³⁷. All BPD treatment-related information will be retrieved up to three years after the date of BPD diagnosis.

Information on somatic comorbidity for calculation of Charlson Comorbidity index³⁹ (CCI) at time of BPD diagnosis, will be retrieved from the DNPR. Data on psychiatric comorbidity will be identified using NPD-Psych. Information on psychiatric comorbidity will be used to define whether each patient had a psychiatric diagnosis prior to BPD diagnosis, after BPD diagnosis or no psychiatric diagnosis. If a psychiatric diagnosis occurs both prior to and after BPD diagnosis, the patient will be defined as having a psychiatric comorbidity prior to BPD diagnosis.

Information on marital status, vital status, and immigration status will be retrieved from the Civil Registration System (CPR)³⁵. Patients that are not alive or have emigrated within three years after BPD diagnosis are considered lost to follow-up and excluded from the cohort. Descriptive data on the socioeconomic status, education level and equivalent available income will be retrieved from Statistics Denmark³⁸. All data comprising each variable will be retrieved from 1th of January 2007 to 31th of December 2017 (three years before and after study period).

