Measures of outcome: The outcome is type of treatment for BPD (surgical, pharmacological and other types of treatment)

Statistics: We will use Fisher's exact test and t-test to compare patients' baseline characteristics with 95% confidence intervals (CI) and p-values. For each treatment type we will use logistic regression model to investigate differences in outcome distribution between patients with and without psychiatric comorbidity. The logistic regressions will be performed with 95% CI adjusted for the following confounders: age, sex, CCI, level of education, equivalent available income, type of BPD (IBD, DBD or UBP) and marital status.

Study 3) Effect of psychiatric comorbidity in pharmacological treatment of BPD.

Aim: 1) To compare dosages of pharmacological treatment in BPD patients with and without the presence of psychiatric comorbidity in a nationwide Danish cohort study in 2010-2014. 2) To compare high vs. low dosages of pharmacological treatment for BPD in patients with BPD and psychiatric comorbidity.

Hypothesis: 1) Patients with BPD and psychiatric comorbidity are prescribed a higher dosage of pain medication for BPD compared with BPD patients without psychiatric comorbidity. 2) BPD patients with a psychiatric comorbidity with a high (defined as above the 50th percentile) vs. low (defined as below the 50th percentile) dosage of pain medication are also prescribed higher dosages of psychiatric medication.

Design and study population: The study will be a nationwide register-based cohort study. The study population consists of patients with BPD that received pharmacological treatment for BPD. In the secondary analysis the study population consists of patients with BPD and a psychiatric comorbidity, who received pharmacological treatment for BPD.

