Procedure: BPD patients will be identified via the DNPR. Pharmacological treatment of BPD will be defined as any treatment with the following drugs: NSAID (ATC: N01A*), Acitomenophen (ATC: N02BE01), Opioids (N02A*)¹³. Pharmacological treatment for psychiatric comorbidity will be defined as any treatment with the following drugs: Antipsychotics (ATC:N05A), Antidepressants (ATC: N06A), Selective Serotonin Reuptake Inhibitors (SSRI) (ATC: N06AB), and anxiolytics (ATC: N5B*)⁴¹. Pharmacological treatment that can be used in the treatment of both BPD and psychiatric disorders will be defined as any treatment with the following drugs: Antiepileptics (ATC: N03A) and Tricyclic antidepressants (ATC: N06AA). All data on pharmacological treatment will be identified using the Register of Medicinal Products Statistics⁷. From time of BPD diagnosis and the following three years, pharmacological treatment for both somatic illness and psychiatric comorbidity in Daily Defined Dosage (DDD) per year will be calculated⁴².

Information on somatic comorbidity for calculation of Charlson Comorbidity index³⁹ (CCI) at time of BPD diagnosis, will be retrieved from the DNPR. Data on psychiatric comorbidity will be identified using NPD-Psych. Information on marital status, vital status, and immigration status will be retrieved from the Civil Registration System (CPR)³⁵. Patients that are not alive or have emigrated within three years after BPD diagnosis are considered lost to follow-up and excluded from the cohort. Descriptive data on the socioeconomic status, education level and equivalent available income will be retrieved from Statistics Denmark³⁸. All data comprising each variable will be retrieved from 1th of January 2007 to 31th of December 2017 (three years before and after study period).

Measures of outcome: Primary outcome is pharmacological treatment in DDDs defined as high (above the 50th percentile and low (below the 50th percentile) of pain medication. Secondary outcome is psychiatric medication in BPD patients with psychiatric comorbidity in DDD's defined according to high (above the 50th percentile) and low (below the 50th percentile) dosages of pain medication.

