Statistics: We will use Fisher's exact test and t-test to compare patients' baseline characteristics with 95% confidence intervals (CI) and p-values. Time dependent Cox regression will be performed separately for patients with specific and unspecific BPD to examine dosage of pharmacological treatment over time comparing patients with and without psychiatric comorbidity. The analysis will be performed with 95% CI and adjusted for the following confounders: age, sex, CCI, level of education, equivalent available income, marital status and the presence of psychopharmacological treatment.

To examine dosage of psychopharmacological treatment over time comparing patients with psychiatric comorbidity and low vs high dose of pharmacological treatment of BPD, time dependent Cox regression will be performed reporting 95% CI and adjusting for the following confounders: age, sex, CCI, level of education, equivalent available income, marital status.

Psychiatric comorbidity in Back Pain Disorders
Risk, treatment and pharmaco-epidemiological analysis

Ethics

All studies will be based on national clinical registries and approval is obtained by The Danish Health Data Board and the Danish Data Protection Agency (18/3337). According to Danish law, further ethical approval is not required for purely registry-based studies. All data will be stored on Statistics Denmark's servers and will be anonymized ensuring no patients can be identified.

PhD Outline

The PhD will be conducted within a timeframe of three years (six semesters).

	1st semester	2nd semester	3rd semester	4th semester	5th semester	6th semester
Data collection	X					
PhD Courses	X	X	X			
Data analysis		X	X	X	X	
Writing articles			X	X	X	X

References

1. Hawker GA. The assessment of musculoskeletal pain. *Clinical and experimental rheumatology* 2017;35 Suppl 107(5):8-12.

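### Study 2 counts psychiatric diagnoses made after treatment as exposure for that treatment, and no stated model uses its prior/after/none variable; Study 3 does not say how timing is handled

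*Combined protocol and SAP*

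**What the plan says.** The definition in Setting and study population applies to all three studies: "the psychiatric diagnosis must be given no earlier than three years prior to back pain disorder diagnosis and no later than three years after". The exposure window is thus six years wide, centred on the BPD date.

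Study 2:
- Hypothesis: "Psychiatric comorbidity affects type of treatment in BPD patients".
- Procedure, outcome window: "All BPD treatment-related information will be retrieved up to three years after the date of BPD diagnosis".
- Procedure, timing: the psychiatric data are to "define whether each patient had a psychiatric diagnosis prior to BPD diagnosis, after BPD diagnosis or no psychiatric diagnosis". A tie rule assigns patients with diagnoses on both sides to the prior group.
- Statistics: for each treatment type, a logistic model is used to "investigate differences in outcome distribution between patients with and without psychiatric comorbidity". The covariates are age, sex, Charlson index, education, income, type of BPD and marital status. Timing is not the exposure, a covariate or a stratifier.
- The four subgroups of aim 2 are also defined by comorbidity present or absent.
- Design and study population names a sub-analysis among BPD patients with comorbidity, but gives it no contrast or model.

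Study 3 covers the same follow-up: "From time of BPD diagnosis and the following three years, pharmacological treatment for both somatic illness and psychiatric comorbidity" is computed in defined daily doses per year. Its Statistics section says: "Time dependent Cox regression will be performed separately for patients with specific and unspecific BPD to examine dosage of pharmacological treatment over time", again with versus without comorbidity. It has no prior/after rule and does not say which variable is time dependent.

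**The concern.** Study 2 asks a directional question, so exposure should come before outcome. As modelled, the odds ratio mixes two things: comorbidity influencing treatment, and treatment (or the course that led to it) being followed by a psychiatric diagnosis. A nationwide sample does not separate them; it only narrows the interval around the mixture.

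The plan's own content makes the reverse path plausible. Opioids are among the outcomes, while substance-use disorders (F10-F19) count as exposure even when diagnosed later; the Introduction cites concomitant substance abuse in up to 43% of BPD patients on opioids. That figure gives no direction, which is why the analysis has to preserve it. Psychologist contacts are also an outcome, and could precede a hospital psychiatric diagnosis that would then be analysed as their cause. The Charlson index, by contrast, is fixed at the BPD date.

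Study 1 is not affected in this way, because comorbidity is its outcome and the question is prevalence.

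**Working it through.** **Windows side by side (Study 2).** Exposure runs from -3 to +3 years and outcome from 0 to +3 years around the BPD date. They overlap for the whole of follow-up, which is half of the exposure window. Nothing in the Statistics section orders the two.

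**Size.** The documents give no rates, treatment proportions or cohort size, so there is no stated figure to reproduce. Everything below is illustration under assumptions.

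Assumed: first psychiatric diagnosis at rate r = 0.01 to 0.02 per year; prior diagnoses k = 1 or 2 times as common as new ones over three years; half of patients treated, at a time u spread evenly over 0-3 years; no effect of comorbidity on treatment; after treatment the diagnosis rate is multiplied by HR.

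- Prior diagnosis: pre = k(1 - exp(-3r))
- Later diagnosis, untreated: 1 - exp(-3r)
- Later diagnosis, treated: mean over u of 1 - exp(-ru - r·HR·(3-u))
- Exposed under the plan: 1 - (1 - pre)(1 - post)

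Worked case, r = 0.015, k = 1, HR = 1.5: pre = 0.0440; post = 0.0440 untreated and 0.0547 treated. Exposed: treated 1 - 0.9560 × 0.9453 = 0.0963; untreated 1 - 0.9560 × 0.9560 = 0.0861. Pooled OR = (0.0963/0.9037)/(0.0861/0.9139) = 1.13. With an assumed 50,000 patients, the cells are about 2,407 and 22,593 (treated), 2,152 and 22,848 (untreated). The standard error of the log OR is 0.031 and the 95% CI is 1.06-1.20.

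| HR after treatment | Pooled OR (true OR 1.00) | Prior versus no prior |
|---|---|---|
| 0.5 to 0.67 | 0.87-0.94 | 1.00 |
| 1 | 1.00 | 1.00 |
| 1.5 | 1.09-1.13 | 1.00 |
| 2 | 1.17-1.27 | 1.00 |
| 3 | 1.35-1.54 | 1.00 |

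If all treatment falls on day 0, HR = 3 with k = 1 gives 2.06-2.13. Even at HR = 1, 15-25% of treated exposed patients were first diagnosed after treatment, and 31-49% of all exposed patients have only a later diagnosis (up to 59% at HR = 3 with treatment spread evenly).

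**Second set of assumptions.** Prior diagnosis 3-5%, later diagnosis 2-5% if untreated, 5-60% treated, and a risk ratio for later diagnosis of 1.25, 1.5 or 2. The pooled null OR is 1.07-1.17, 1.15-1.34 or 1.30-1.71; prior versus no prior stays at 1.00.

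**Prior versus none.** Dropping after-only patients from the comparator conditions on the future. With treatment on day 0 the null OR is exp(3r(HR - 1)) = exp(0.09) = 1.09 at r = 0.015, HR = 3.

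**Late-recorded illness.** Take a true OR of 2.0, r = 0.015, k = 1, and 50% treated without illness (so two thirds with it). Let f be the share of after-only patients who were already ill when treated.

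| f | Pooled OR | Prior versus no prior |
|---|---|---|
| 0 | 1.41 | 2.00 |
| 0.5 | 1.67 | 1.97 |
| 1 | 2.00 | 1.94 |

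**The case against.** The best defence is that a hospital diagnosis date is not an onset date. The Introduction concedes of the registry that "it does not provide complete data from the primary care sector selecting only severe psychiatric diagnosis", and the definition includes personality, developmental and childhood-onset disorders, where recording may trail onset by years. A month-34 diagnosis need not mean that the patient was well in month 2. This stands as a reason to keep the wide window as a sensitivity analysis. It does not justify making it primary: if every after-only patient was already ill, prior versus no prior loses little (1.94 against 2.00), whereas if none was, the pooled contrast falls to 1.41.

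Aim 1 of Study 2 and its Statistics section can also be read as purely descriptive comparisons. The hypothesis, however, says that comorbidity affects treatment.

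The timing variable and tie rule show that the authors saw the issue, and prior versus after is an obvious contrast for the sub-analysis among comorbid patients. But none is stated, and it would not repair the main model.

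Three limits on the illustration stand. No document figure supports HR above 1, and values below 1 bias the estimate downwards, so the direction is unknown. The confidence interval depends on half of patients being treated: for a treatment given to 5% (50,000 patients, r = 0.015, k = 1, HR = 1.5) it is 0.99-1.30, and it includes 1 in five of the six r and k combinations. Finally, fixing exposure at the BPD date also reclassifies patients diagnosed after BPD but before treatment, whose order was correct.

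**Conclusion.** The concern holds for Study 2. Followed as written, the plan counts diagnoses made after treatment as exposure for that treatment, under a directional hypothesis, and no stated model uses the variable that would recover the order. This conclusion rests on the text alone. The size does not: the bias is nil if treatment and later diagnosis are unrelated, roughly 10% to 50% on the odds ratio if treated patients are later diagnosed at 1.5 to 3 times the rate, and downwards if they are diagnosed less often. All of this rests on assumed rates.

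For Study 3 the finding is only missing specification. A time dependent Cox model may already be meant to carry time-varying comorbidity, but the plan does not say so. This should be fixed before analysis.

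**What to change.** **Study 2.** Make the primary exposure a psychiatric diagnosis in the three years up to and including the BPD date, compared with all patients without such a diagnosis, and use it for the four subgroups of aim 2. Keep after-only patients in the comparator and also report them separately as descriptive. Retain the six-year definition as a sensitivity analysis. State what the sub-analysis among comorbid patients compares.

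**Study 3.** Either use the same baseline exposure, or enter comorbidity as time-varying from its diagnosis date so that only later dosage counts as exposed. State which.

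**Study 1** can keep its window.

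**Cost.** Study 2 needs a change of wording only, including a rule for same-day diagnoses, which the present prior/after split leaves unassigned. Study 3 needs the timing variable derived from the 2007-2017 registry dates already requested; the time-varying option adds some programming. The price is about 31-49% fewer exposed patients under the assumed rates (up to 59% at three times the rate), in a nationwide cohort. Some illness not yet diagnosed in hospital, and some diagnosed between BPD and treatment, will be classed as unexposed.
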